10.4.4 Safety assessment criteria

Adverse events after vaccination shall be judged according to grading criteria of *Guiding Principles of Grading Standards for Adverse Events in Clinical Trials of Preventive Vaccines* (National Drug Administration No. 102 of 2019)

Table 8. Rating Scale of Reaction Events at the Inoculation Site (Local)

Symptom/sign	Grade 1	Grade 2	Grade 3	Grade 4
Pain	No or minor impact on physical activities	Impact on physical activities	Impact on daily life	Loss of basic self-care ability, or hospitalization
Induration*, swelling**#				
Aged >14	2.5-<5 cm in diameter, or 6.25-<25 cm ² in area, and not or minor impact on daily life	5-<10 cm in diameter or 25-<100 cm ² in area, and impact on daily life	≥10 cm in diameter, ≥100 cm ² in area, ulceration, secondary infection, phlebitis, aseptic abscess, wound drainage, or severe impact on daily life	Abscess, exfoliative dermatitis, dermal or deep tissue necrosis
Rash*, areola**#				
Aged >14	2.5-<5 cm in diameter, or 6.25-<25 cm ² in area, and not or minor impact on daily life	5-<10 cm in diameter or 25-<100 cm ² in area, and impact on daily life	≥10 cm in diameter, ≥100 cm ² in area, ulceration, secondary infection, phlebitis, aseptic abscess, wound drainage, or severe impact on daily life	Abscess, exfoliative dermatitis, dermal or deep tissue necrosis
Pruritus	Pruritus at the inoculation site, relieved spontaneously or within 48 hours after treatment	Pruritus at the inoculation site, not relieved within 48 hours after treatment	Impact on daily life	NA
Cellulitis	NA	Non-injection therapy (e.g., oral antibacterial, antifungal and antiviral medication) is required	Intravenous injection therapy (e.g., intravenously antibacterial, antifungal and antiviral medication) is required	Sepsis, or tissue necrosis, etc.

Note: *In addition to measuring the diameter directly for grading evaluation, subsequent changes to the measurement results should also be recorded.

**The maximum measured diameter or area should be used.

#The indicators with higher grades should be selected based on the functional grade and actual measurement results for the evaluation and grading of induration, swelling, rash and areola.

Table 9. Vital Sign Rating Scale

Vital signs	Grade 1	Grade 2	Grade 3	Grade 4
Fever* [axillary temperature (°C)]				
Aged >14	37.3~<38.0	38.0~<38.5	38.5~<39.5	≥39.5, lasting for more than 3 days

Note: *Axillary temperature is usually adopted in China, and converted to oral and rectal temperature when necessary. Generally, oral temperature = axillary temperature +0.2°C; rectal temperature = axillary temperature + (0.3-0.5°C). The cause should be identified early in case of a persistent high fever.

Table 10. Rating Scale of Adverse Events at the Non-inoculation Site (Systemic)

Symptom/sign of organ system	Grade 1	Grade 2	Grade 3	Grade 4
Gastrointestinal system				
Diarrhea	Minor or transient, 3-4 times/day, abnormal stool appearance, or minor diarrhea for less than 1 week	Moderate or persistent, 5-7 times/day, abnormal stool appearance, or diarrhea for > 1 week	> 7 times/day, abnormal stool appearance, or hemorrhagic diarrhea, orthostatic hypotension, and electrolyte imbalance, which require intravenous infusion >2L	Hypotensive shock, which requires hospitalization
Anorexia	Loss of appetite, but without decrease of food intake	Loss of appetite, with decrease of food intake but no significant weight loss	Loss of appetite and significant weight loss	Interventions are required (e.g., gastric tube feeding and parenteral nutrition)
Emesis	1-2 times/24 hours and no impact on activities	3-5 times/24 hours or imitation of activities	> 6 times within 24 hours or need for intravenous rehydration	Need for hospitalization or other means of nutrition due to hypotensive shock
Nausea	Transient (<24 hours) or intermittent, and generally normal food intake	Persistent nausea results in decreased food intake (24-48 hours)	Persistent nausea results in almost no food intake (>48 hours) or the need for intravenous rehydration	Life threatening (e.g., hypotensive shock)
Musculoskeletal and connective tissue				
Myalgia (non-inoculation site)	No impact on daily activities	Slight impact on daily activities	Severe myalgia, with severe impact on daily activities	Emergency or hospitalization
Nervous system				
Headache	No impact on daily activities and no need for treatment	Transient; slight impact on daily activities and possible need for treatment or intervention	Severe impact on daily activities and need for treatment or intervention	Refractory; need for emergency treatment or hospitalization
Respiratory system				
Cough	Transient; no need for treatment	Persistent cough, with effective treatment	Paroxysmal cough, with uncontrollable treatment	Emergency or hospitalization
Dyspnea	Dyspnea during exercise	Dyspnea during normal activities	Dyspnea at rest	Dyspnea, and need for oxygen therapy, hospitalization or assisted breathing
Skin and subcutaneous tissue				
Abnormal skin and mucous membranes	Erythema/pruritus/color changes	Diffuse rash/maculopapule/dryness/desquamation	Blister/exudation/desquamation/ulcer	Exfoliative dermatitis with mucosal involvement, erythema multiforme, or suspected Stevens-Johnsons syndrome
Immune system				
Acute anaphylases**	Local urticaria (blisters) not requiring treatment	Local urticaria requiring treatment, or minor angioedema not requiring treatment	Extensive urticaria or angioedema requiring treatment, or minor bronchospasm	Anaphylactic shock, life-threatening bronchospasm or laryngeal edema
Others				

Fatigue	No impact on daily activities	Impact on normal daily activities	Severe impact on daily activities and inability to work	Emergency or hospitalization
---------	-------------------------------	-----------------------------------	---	------------------------------

Note: ** refers to type I hypersensitivity.

For adverse events not covered in the above scale, the intensity assessment should be performed according to the following criteria:

Grade 1 Mild: transient (<48h) or slight discomfort, which does not affect activities and not require treatment;

Grade 2 Moderate: mild or moderate activity limitation, which may require medical attention, no treatment, or only mild treatment;

Grade 3 Severe: significant restriction of activities, which requires medical attention, treatment, and possibly hospitalization;

Grade 4 Critical: it may be life-threatening, severely restricts activities, and requires monitoring and treatment.

Grade 5 Death

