8.10 Study Suspension/Early Termination

Criteria for suspension:

- The trial will be suspended in the event of 1 grade 4 or serious adverse event that may be related to vaccination during the study period;
- The trial will be suspended when more than 15% of subjects have experienced adverse events of grade 3 or above.

If the occurrence of adverse events meets the set criteria for suspension, firstly, the trial shall be suspended. Then, temporary DSMB meeting shall be held.

And the AE shall be reported to the national drug regulatory authority and the ethics committee, and the subject shall be notified. Based on the analysis of the correlation between adverse events, hazard degree and safety risks, investigation reports shall be formed and reported to relevant parties for them to decide whether to restart the clinical trial or not.

Criteria for early termination:

- The trial will be terminated early when there is 1 death that may be related to vaccination during the study period;
- When more than 30% of subjects have adverse events of Grade 3 and above, the investigators, sponsors and the data security monitoring committee will discuss together to decide whether to terminate the trial early;
- The sponsor requests full termination of the trial with justification;
- The administrative authorities request full termination of the trial with justification.
- The ethics committee requests full termination of the trial with justification.

9. Subject Population

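### Table 9 gives no grade to an axillary temperature of 39.5°C or more lasting 3 days or less, so the highest short fevers have no defined place in the Grade 3-or-above results

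*Protocol*

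**What the plan says.** Section 10.4.4 says that adverse events are judged by a named national grading guideline, and then prints the scales to be used.

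- **Table 9, fever (axillary, over 14 years), Grades 1 to 4:** "37.3~<38.0 38.0~<38.5 38.5~<39.5 ≥39.5, lasting for more than 3 days". Only the Grade 4 cell carries a duration condition.
- **Note under Table 9:** it covers conversion between measurement sites and adds that "The cause should be identified early in case of a persistent high fever". It contains no grading rule.
- **Table 10, emesis:** Grade 2 is "3-5 times/24 hours or imitation of activities" (I read the printed word as limitation). Grade 3 is "> 6 times within 24 hours" or a need for intravenous rehydration.
- **Generic scale after Table 10:** introduced with "For adverse events not covered in the above scale, the intensity assessment should be performed according to the following criteria".

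The grades are used in two places. Section 8.10 states "The trial will be suspended when more than 15% of subjects have experienced adverse events of grade 3 or above", has a further rule at more than 30%, and suspends the trial for a single Grade 4 event that may be related to vaccination. Section 10.7.4.4 calculates the number and incidence of Grade 3-or-above events by group (overall and vaccine-related), describes severity, and lists the Grade 3-or-above events.

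**The concern.** A severity scale should give every value a grade, and a worse value should never rank below a better one. Table 9 does neither above 39.5°C: a one-day fever of 39.4°C is Grade 3, and a one-day fever of 40.0°C is nothing. The effect runs in one direction, because the affected events are the highest fevers that settle within 3 days. Followed to the letter, the table leaves them out of the Grade 3-or-above results. Where an assessor supplies a grade by judgement, the results depend on who graded.

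**Working it through.** The plan states no figure on this point, so there is none to reproduce. The check is one of coverage.

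**Fever.** Inputs are the four cells of Table 9, coded as conditions on temperature T and duration D:

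- Grade 1: 37.3 ≤ T < 38.0
- Grade 2: 38.0 ≤ T < 38.5
- Grade 3: 38.5 ≤ T < 39.5
- Grade 4: T ≥ 39.5 and D > 3 days

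| T (°C) | D = 1 | D = 2 | D = 3 | D = 4 |
|---|---|---|---|---|
| 38.4 | 2 | 2 | 2 | 2 |
| 38.5 | 3 | 3 | 3 | 3 |
| 39.4 | 3 | 3 | 3 | 3 |
| 39.5 | none | none | none | 4 |
| 40.0 | none | none | none | 4 |
| 41.0 | none | none | none | 4 |

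From 37.3 to below 39.5°C there is no gap. The uncovered region is exactly T ≥ 39.5 with D ≤ 3 days.

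**Does anything else in the protocol close it?**

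1. The note under Table 9 deals with measurement site and the cause of persistent fever, not with grade.
2. The notes under Table 8 on using the maximum measurement and the higher grade are confined to induration, swelling, rash and areola.
3. The generic scale is for events outside the tables, and fever is in them. It also takes no account of temperature. A 40.0°C fever under 48 hours that neither limits activity nor needs treatment would come out as Grade 1, still outside Grade 3 or above.
4. Reading the comma in "≥39.5, lasting for more than 3 days" as 'or' fills the hole, but then 37.4°C for 4 days is both Grade 1 and Grade 4.

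**Emesis.** The count bands are 1-2, "3-5 times/24 hours" and more than 6. A count of 6 falls in none. With activity limitation, 6 episodes are Grade 2; with intravenous rehydration, Grade 3. Only 6 episodes with neither, and with no Grade 4 criterion, has no grade. The diarrhea row in the same table is contiguous (3-4, 5-7, more than 7).

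**Size.** Table 1 gives 4 cohorts × (100 + 100) = 800 vaccine recipients out of 1000 subjects. The rates below are assumptions, because the documents give none.

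- Expected number affected: 0.5% × 800 = 4; 2% × 800 = 16.
- Chance of at least one, 1 − (1 − p)^800: p = 0.1% gives 55%; 0.2% gives 80%; 0.5% gives 98%; 1% gives more than 99.9%.
- In one dose arm of 100, each affected subject with no other Grade 3-or-above event is 1/100 = 1 percentage point of that arm's Grade 3-or-above incidence.
- Thresholds in 8.10, taking all 1000 subjects as the denominator (an assumption): more than 15% needs 151 subjects and more than 30% needs 301. The 4 to 16 subjects are 0.4% to 1.6% of 1000.

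**The case against.** The strongest reply is that little would be lost in practice.

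- **Reporting.** Section 10.4.8 lists fever among the early suspected COVID-19 symptoms to be reported at all times, whatever the grade, and followed until resolved. A reader might infer that these fevers could escape notice because they cannot be graded on the day. The documents do not support that.
- **Endpoints.** The safety endpoints in 8.7.2 are incidences of adverse events and serious adverse events, and an ungraded fever counts in the first. Section 10.7.4.4 names Fisher's exact test for all, related and unrelated events, not for Grade 3 or above.
- **Data handling.** A reader might infer that a grade programmed from diary temperatures would come back missing, or that the dose comparison would be biased. The protocol does not say that grades are programmed. Bias between doses would also need short high fevers to differ by arm, on which there is no information.
- **Single-event rule.** A reader might infer that a short fever of 39.5°C or more could trigger suspension as Grade 4. Literally it cannot, because the duration condition is not met. A possibly related event that qualifies as serious triggers suspension regardless of grade.
- **Common sense.** A fever reaching 39.5°C passes through the Grade 3 band, so an assessor may well call it Grade 3. That is plausible, but the protocol states no such rule, and another assessor could use the generic scale or disregard the duration condition.
- **Source.** The cited guideline is not at hand. It may contain the same gap, close it, or have been mistranslated here. The printed table is still what sites will work from.

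These replies limit the consequences. They do not supply the missing grade.

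**Conclusion.** The gap in Table 9 is real. Temperatures of 39.5°C or more for 3 days or less have no grade, the scale is not monotone, and nothing else in the protocol repairs it. Read literally, such fevers are absent from the Grade 3-or-above incidence and listing and from the counts in 8.10; otherwise their grade is left to the assessor. The size is unknown. On the assumed rates, a handful of subjects would be affected: noticeable in a 100-subject arm's severity table, and probably immaterial to the 15% and 30% thresholds. The vomiting gap is a trivial companion, limited to exactly 6 episodes with no other criterion in the row met. The finding rests on the table as printed and cannot say whether the cited guideline has the same gap.

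**What to change.** Reconcile Tables 9 and 10 with the national grading guideline cited in 10.4.4. Every combination of temperature and duration from 37.3°C upwards, and every vomiting count, should map to exactly one grade, and a higher temperature should never be left ungraded. Use the same cut-points wherever grades are recorded or derived. Which grade applies to the uncovered values is for the sponsor to decide, since it feeds the suspension criteria; this review does not propose one.

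The cost is two table cells and a matching check of the eCRF. Sample size, visits and randomization are unaffected. The Grade 3-or-above rate may become slightly less favourable once these fevers have a defined grade.

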10.4.5 Outcomes of adverse events

The outcomes of adverse events include: (1) recovery, (2) non-recovery, (3) recovery with sequelae, (4) death, (5) loss of follow-up/unknown.

10.4.6 Relationship between adverse events and experimental vaccines

Certainly unrelated: other factors contribute to the occurrence of an adverse event, and there is sufficient evidence that the adverse event/event is caused by other factors instead of vaccination.

Possibly unrelated: an adverse event may be caused by other factors, such as the subject's clinical condition, other treatments or concomitant medications, and it is inconsistent with known adverse reactions of vaccination.

Possibly related: an adverse event is consistent with known information of the experimental vaccine, follows a reasonable time sequence with vaccination, and/or has occurred previously during vaccination. Moreover, it has a causal link with the experimental vaccine, but may also be related to other factors.

Very likely related: an adverse event is consistent with known information of the experimental vaccine, and has a causal relationship with the experimental vaccine which cannot be explained by other factors, such as the subject's clinical conditions, other treatments, or concomitant medications.

Certainly related: an adverse events is consistent with known information of the experimental vaccine, and has a causal relationship with the experimental vaccine which cannot be explained by other factors, such as the subject's clinical conditions, other treatments, or concomitant medications. In addition, adverse events are repeated when subjects are administered with the experimental vaccine again.

Adverse events that are certainly unrelated and possibly unrelated are counted as unrelated to the inoculation of experimental vaccine; while adverse events that are possibly related, very likely related and certainly related are counted as related to the inoculation of experimental vaccine.

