10.4 Safety Observation

10.4.1 Definition of Adverse Events and Adverse Reactions

Adverse events: refer to all adverse medical events occurring to the subjects after receiving the investigational drugs, which are shown in symptoms, diseases or laboratory abnormalities. However, it is not always possible to deduce causal relationship between them and the experimental vaccines.

Adverse reactions: refer to all hazard or unexpected reactions for human that may be related to the experimental vaccines in clinical trials. There is at least a reasonable probability of a cause relationship between the experimental vaccines and the adverse event, that is, the correlation cannot be ruled out.

Serious adverse event: refer to all adverse medical events occurring to the subjects after receiving the investigational drugs, which are shown in death, life-threatening, permanent or serious disability, or the subjects need hospitalization or extended hospitalization and congenital abnormality or birth defect.

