10.4.7 Report of severe adverse events

Upon becoming aware of any severe adverse events (SAE), the investigator should promptly (within 24 hours) report all SAEs in writing to the sponsor and submit follow-up reports.

Upon receipt of safety-related information from any source, the sponsor should conduct an analytical assessment, including severity, association with the experimental drug, and identification of an expected event. The sponsor should report suspicious and unexpected severe adverse reactions (SUSAR) to the investigator, the clinical trial institution and the ethics committee as soon as possible. Meanwhile, the sponsor should report SUSARs to the National Medical Products Administration and the health authorities. For fatal or life-threatening SUSARs, the sponsor should report to the National Medical Products Administration immediately after first being informed and within 7 natural days, and report relevant follow-up information within the following 8 days; for non-fatal or non-life-threatening SUSARs, or information about other potential severe safety risks, the sponsor should report to the National Medical Products Administration immediately after first being informed and within 15 natural days.

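### Section 10.4.6 builds expectedness into causality, so a new kind of adverse event can be counted as unrelated, fit two opposing grades, or fit none

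*Protocol*

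**What the plan says.** Protocol section 10.4.6 has five grades.

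- *Certainly unrelated*: there is sufficient evidence of another cause.
- *Possibly unrelated*: another cause is possible, "and it is inconsistent with known adverse reactions of vaccination".
- *Possibly related*: the entry opens with agreement with known information and continues "follows a reasonable time sequence with vaccination, and/or has occurred previously during vaccination". It then adds a causal link and allows that other factors may contribute.
- *Very likely related*: "Very likely related: an adverse event is consistent with known information of the experimental vaccine, and has a causal relationship with the experimental vaccine", with no other explanation.
- *Certainly related*: "Certainly related: an adverse events is consistent with known information of the experimental vaccine, and has a causal relationship with the experimental vaccine", with no other explanation and recurrence on re-administration.

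The grades are then reduced to two classes: "Adverse events that are certainly unrelated and possibly unrelated are counted as unrelated to the inoculation of experimental vaccine". The other three count as related.

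Section 10.4.1 defines an adverse reaction more widely. It covers unexpected reactions, and its test is a reasonable probability of a causal relationship, "that is, the correlation cannot be ruled out". It has no condition about known information.

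Relatedness is used in section 8.10 ("The trial will be suspended in the event of 1 grade 4 or serious adverse event that may be related to vaccination", and early termination after one death described in the same terms), in 9.4(1), which concerns later doses after a causally associated SAE, in the SUSAR provisions of 10.4.7, and in the related and unrelated AE tables of 10.7.4.4.

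**The concern.** Causality asks whether the vaccine caused the event. Expectedness asks whether such an event was already known. Section 10.4.6 lets the second question help decide the first, so being new counts against being related.

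That is awkward for a vaccine at this stage. The product information shown in the protocol is limited: animal data in section 5, a preliminary phase I check 7 days after the first high dose, and literature on similar vaccines in 14.1.

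The rules that depend on relatedness in 8.10 act on a single event, so one grade can decide whether they act. Section 10.7.5 plans no interim safety analysis, and 10.9 ties DSMB assessment to that section. The ad hoc DSMB meeting that follows a suspension is therefore the main DSMB route this protocol describes, although a separate charter is mentioned and not shown.

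**Working it through.** The protocol gives no figure on this point, so there is none to reproduce. The check applies the criteria of 10.4.6 to a test case.

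**Step 1. Test case.** A new event that agrees with neither known vaccine information nor known reactions, with plausible timing and a causal link. Two features are varied: whether another cause is conceivable, and how the and/or in *possibly related* is read. On the strict reading, agreement with known information is required. On the lenient reading, it is one of several alternatives.

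| Reading of *possibly related* | Other cause conceivable? | Grades that fit | Counted as |
|---|---|---|---|
| Strict | No | none of the five | undefined |
| Strict | Yes | *possibly unrelated* | unrelated |
| Lenient | No | *possibly related* | related |
| Lenient | Yes | *possibly unrelated* and *possibly related* | both |

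Recurrence on re-administration changes none of the four rows. *Very likely* and *certainly related* stay closed throughout, because agreement with known information is joined to the rest by *and*. Only one of the four rows gives a clear classification as related.

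**Step 2. Against 10.4.1.** The same event meets the definition of an adverse reaction in 10.4.1 in all four rows, since unexpected reactions are included and the relationship cannot be excluded. The two sections also set different thresholds: *possibly related* asserts a causal link, whereas 10.4.1 asks only that one cannot be excluded. They conflict however the and/or is read.

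**Step 3. Which event-based rules in 8.10 depend on causality.**

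| Rule | Depends on relatedness? |
|---|---|
| Suspension: one Grade 4 event or SAE | yes |
| Suspension: more than 15% of subjects with Grade 3+ | no |
| Termination: one death | yes |
| Joint discussion of termination: more than 30% of subjects with Grade 3+ | no |

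**Step 4. Can the percentage rules serve as a backstop?** Taken over all 1000 subjects (an assumption), they need more than 0.15 × 1000 = 150 and more than 0.30 × 1000 = 300 subjects. Table 1 gives 4 × (100 + 100) = 800 vaccinees. For a new severe toxicity with an assumed rate p, the chance of at least one case is 1 − (1 − p)^800:

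| Assumed p | Expected cases, 800p | Chance of at least 1 case | Chance that it alone gives 151 or more |
|---|---|---|---|
| 0.25% | 2 | 86.5% | effectively 0 |
| 0.5% | 4 | 98.2% | effectively 0 |
| 1% | 8 | 99.97% | effectively 0 |

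The rates are illustrative and not from the protocol. At such rates the trial would very probably see a case, and only the rules that depend on relatedness could respond to it.

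**Step 5. SUSAR reporting.** Section 10.4.7 sends every SAE to the sponsor within 24 hours, whatever its grade. The sponsor assesses association and expectedness as separate items, and other potential severe safety risks are also reportable. An investigator's grade of *possibly unrelated* does not close this route. However, 10.4.7 gives no association criteria of its own, so the sponsor might fall back on 10.4.6.

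**The case against.** The strongest reply is that the split is binary and the lowest related grade is enough to open it. If the and/or joins alternatives, timing plus a causal link makes a new event *possibly related*, and it does not matter that the upper two grades are closed. This stands in part: a reader might infer that no new event can be graded related, and the text does not support that. But on the same reading, a new event with a conceivable other cause also fits *possibly unrelated*, on the opposite side of the split.

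Second, the scale uses two undefined terms, known information in the related grades and known adverse reactions in *possibly unrelated*. An event absent from the list of reactions could still agree with what is known of the antigen or adjuvant. That stands as a limit: the test case is an event that agrees with neither.

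Third, novelty alone never makes an event unrelated, because *possibly unrelated* also needs another possible cause. That is correct. Without one, the worst outcome is an event with no grade, and 10.4.1 could then be used to settle it.

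Fourth, a reader might infer that the stopping rules as a whole, or SUSAR reporting, are disabled. Neither is supported. Two of the four event-based rules ignore causality, although they are no practical backstop for a rare event, and 10.4.7 has the sponsor make its own assessment: "The sponsor should report suspicious and unexpected severe adverse reactions (SUSAR) to the investigator". Section 8.10 also does not cite the 10.4.6 scale, so it is not established that the scale governs it. Section 10.7.4.4 further tabulates all AEs and all Grade 3+ AEs and lists SAEs, so the event stays visible.

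**Conclusion.** The concern holds as an internal contradiction between 10.4.6 and 10.4.1 and as a defect in the scale. Agreement with known information is mandatory in two of the three related grades and ambiguous in the third, and disagreement with known reactions counts towards an unrelated grade. For a new event, the scale gives a clear related grade in one of the four combinations examined.

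What it can affect is limited to uses of relatedness: the two one-event rules in 8.10, 9.4(1), and the related/unrelated tables. SUSAR reporting is at most weakened. The effect on 8.10 and 9.4(1) assumes that relatedness there is judged by 10.4.6. This is plausible, since it is the only graded scale in the protocol, but it is not stated. No misgrading rate can be derived from the document. The consequence is potentially large only because a single event is decisive.

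**What to change.** Reconcile 10.4.6 with 10.4.1:

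- Remove agreement with known information as a condition of the related grades, and disagreement with known reactions as a condition of *possibly unrelated*.
- Leave that comparison to the expectedness assessment, which 10.4.7 already lists separately from association.
- Reword the five grades so that every event fits exactly one, and resolve the and/or in *possibly related*.

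The sponsor should also reconcile 8.10 and 9.4(1) with 10.4.1 and 10.4.6 by stating which definition of relatedness they use. What the stopping or revaccination rule should be is a clinical decision for the sponsor and investigators, and this point does not propose one.

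The cost is a wording amendment, brief site retraining on the causality form, and somewhat more events classed as related. The last is not trivial if 8.10 is tied to the revised scale, because one event there can suspend or end the trial.
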